Please note that beginning July 1, 2020, per HB1570, we will recruit individuals aged 18-55. This law "Provides an exception to the law prohibiting possession of tobacco products, nicotine vapor products, or alternative nicotine products by a person less than 21 years of age when such possession is part of a scientific study being conducted by an organization for the purpose of medical research to further efforts in cigarette and tobacco use prevention and cessation and tobacco product regulation, provided that such medical research has been approved by an institutional review board pursuant to applicable federal regulations or by a research review committee." We will not enroll any participants under the age of 21 until after July 1, 2020.

5. * List the study exclusion criteria:

Individuals with the following self-reported current, diagnosed medical condition(s) will be excluded automatically: uncontrolled high blood pressure (i.e., self-reported and/or observed at screening; BP above 160/100), recent heart attack/stroke, coronary heart disease, severe immune system disorders (e.g., HIV/AIDS, multiple sclerosis), respiratory disorders (e.g., COPD, asthma), kidney diseases, liver diseases (e.g., cirrhosis), or seizures.

Individuals with other self-reported current, diagnosed medical conditions (e.g., diabetes, thyroid disease, lyme disease) will be considered for exclusion after consultation with the PI and medical monitor. Participants with any medical condition/medication that may affect participant safety, study outcomes, or biomarker data will be excluded based on these consultations.

Participants with self-reported current, diagnosed psychiatric conditions, and who are currently under the care of a physician for psychiatric conditions, or who report current psychiatric treatment or psychotropic medication use will be excluded.

Individuals with past-month use of other illicit drugs including cocaine, opioids, benzodiazepines, and methamphetamine will be excluded.

Individuals who report using marijuana ≥ 16 days in the past 30 and/or alcohol ≥ 26 days in the past 30 days will be excluded.

Those who intend to quit tobacco/nicotine use in the next 30 days will be excluded and referred to cessation treatment.

Use of other tobacco products (other than cigarettes) at any frequency will NOT be exclusionary.

Women will be excluded if they are breast-feeding or test positive for pregnancy (by urinalysis) at the screening.

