Participants who choose not to answer questions related to the inclusion/exclusion criteria will be excluded.

In addition, participants who have previously participated in a study with exactly the same manipulations of ECIG type, setting, and liquid concentration will be excluded. Specifically, participants who have participated in HM20018580 will not be eligible to participate in this protocol. Staff from this protocol will work with staff from HM20018580 (who are also listed on this protocol) to assure that there is no cross-participation between participants.

6. * Will individuals with limited English proficiency be included in or excluded from this research?

- Included
- Excluded - safety concerns if participants are unable to communicate with the study team
- Excluded - instruments/measures only validated in English**
- Excluded - no prospect of direct benefit to individual participants
- Excluded - minimal risk study
- Excluded - lack of budget/resources for translation and interpretation [provide an explanation in next question]
- Excluded - other reason [provide an explanation in next question]

7. Justify the inclusion and exclusion criteria if you are either targeting, or excluding, a particular segment of the population / community. Provide a description of the group/organization/community and provide a rationale.

We are excluding individuals (<18 years old) as this group includes children for whom research risks may differ compared to those 18 or older. This younger age group is also likely to differ in important ways compared to individuals aged 18 and older including likelihood of residing with a guardian/parent which may impact their response to research questions of interest. We also exclude pregnant/breastfeeding women as tobacco/nicotine use is dangerous to a fetus/child. We exclude individuals with certain health conditions that may be exacerbated by tobacco product administration and/or tobacco/nicotine abstinence. We also exclude individuals with drug use histories that may raise the risk of participation or affect the quality of data collected in the study.

Background, Rationale & Goals Section Complete

1 Progress:
1.1 **PROJECT SETUP**

BACKGROUND, RATIONALE & GOALS

- ③ RESEARCH PLAN
- ④ CONSENT PLAN
- ⑤ RISKS, PRIVACY & CONFIDENTIALITY
- ⑥ POPULATIONS WITH SPECIAL CONSIDERATIONS
- ⑦ INSTITUTIONAL REQUIREMENTS
- ⑧ DOCUMENTS

Click Continue below to go to the next section

Study Procedures

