6. * Since a separate protocol document is not uploaded, describe the proposed research using language understandable to those IRB committee members whose expertise is not scientific. The description must include:

- 1. A statement explaining the study design**
- 2. A detailed description of all the procedures that will be followed to carry out the study, preferably in sequential order, and in sufficient detail that the study's methods could be replicated**
- 3. The schedule and frequency of when and how procedures will be conducted (e.g. in person, online, phone, paper, etc.)**
- 4. A description of all research measures/tests/interventions that will be used, including analyses/tests conducted on specimens/biological samples (if applicable)**

See the help text for additional guidance

Overview. This study involves 40 CIG users who will complete 5, within-subject, laboratory conditions that differ by the product used: 1) 30 W; 0 mg/ml; 2 sec puff, 2) 30 W; 6 mg/ml; 2 sec puff, 3) 30 W; 15 mg/ml; 2 sec puff, 4) 30 W; 30 mg/ml; 2 sec puff, and 5) own brand (tobacco cigarette). The first 4 ECIG conditions will be Latin-square ordered and single blinded such that the participants will not know which condition is administered in each ECIG session. The last condition for all subjects will be their own brand CIG.

Participants. A total of 40 adults (ages 18-55) who currently use CIGs will be enrolled. We will attempt to recruit an equal number of men and women of diverse racial/ethnic backgrounds, although this study is not intended to address gender or race/ethnic differences.

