Recruitment and Enrollment. Potential participants will be recruited by IRB-approved advertisements, as well as referral from current participants. Once initial screening is completed (either over the phone or via the internet), potentially eligible participants will be invited to the lab to complete in-person informed consent, additional screening, and familiarization with study procedures (approximately 2 hrs, \$15 compensation). Once participants have been seated in a private study room, research staff will communicate with the participants primarily using Zoom as an intercom, to speak/interact with participants. Prior to in-person data collection, staff will review the informed consent in person and/or using a Powerpoint/video tool to ensure they understand the study, its risks and benefits, and their rights as research participants. Participants will have the opportunity to ask questions to the research staff, prior to signing the consent document. Following documentation of informed consent, participants will complete baseline measures to confirm eligibility, have their blood pressure and heart rate checked, provide a urine sample that will be tested for cotinine level (to confirm current smoking status) and pregnancy (women only), and provide a exhaled breath carbon monoxide (eCO) sample. Age will be verified by asking participants to provide some form of identification that includes a date of birth. Photos of participant cigarette packs will be taken. All study procedures will be reviewed/practiced using approved measures and/or Powerpoint/video-based tools. Participants will complete the Minute Discounting Task and finally the Balloon Analogue Risk Task (BART). Depending upon task performance, participants will receive up to \$40 in compensation for the actual amount earned at the end of the BART task.

New recruits will replace participants who do not complete the study. Accrual ends when the required number of completers (N=40) is reached.

Individuals whose blood pressure levels are elevated (>=140 mmHg systolic or >=90 mmHg diastolic) during screening or at a session will be provided with a blood pressure information sheet by the research staff (see study document). This sheet will be provided at the first instance of elevated blood pressure observed during the study.

Products. Own brand tobacco cigarettes will be purchased locally following enrollment by VCU approved staff. For all

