other sessions we will provide ECIG liquid at 0 mg/ml, 6 mg/ml, 15 mg/ml, or 30 mg/ml; nicotine and an “open system” ECIG (e.g., Kanger Sub Box Mini C; ECIG device modified by Project 1 team) set to 30 watts. All liquids used will be unflavored and unsweetened. ECIG puffs will be limited to 2 seconds in duration for all of these sessions using hardware and/or a computer program. Own brand cigarette puffs will be allowed to vary in duration (not controlled).

Procedure. The first four sessions will be identical, except for the product given to the participant. The fifth session will be their own brand session. This session will end early, as described below.

Each session, participants will be asked to refrain from tobacco/nicotine use for ≥ 12 hours and drinking caffeinated beverages for 1 hour prior to their scheduled session with verification of tobacco/nicotine use status upon arrival at the laboratory for each session. More specifically, upon arrival at the laboratory for each session, participants’ breath eCO will be measured to ensure compliance with the overnight abstinence criteria (eCO must be either < or equal to half of the eCO [ppm] that the participant had at the in-person screening visit, or, if 10 ppm or less at screening, it must be equal to or less than 5 ppm before a session can begin). We are no longer requiring 1-hr food abstinence prior to each session as this design detail was originally included to reduce the impact of a recent meal/caloric intake on primary outcomes/participant responding. We reconsidered this design detail in consultation with our study timeline and other protocols ongoing among our research team and decided that this food abstinence requirement likely has less impact than that from caffeine consumption on our primary outcomes and is more burdensome to participants. Research staff will use Zoom, as an intercom to communicate with participants whenever possible during sessions.

At the start of the session, participants will be asked about symptoms experienced since last visit and their use of other substances in their ECIG. Answers given about respiratory and gastrointestinal symptoms will be compared to the participants’ previous answers, and if any symptoms have become more frequent or more severe, [name] will be asked to review the symptoms. In some cases, we may contact [name] to determine if a session can proceed.

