Next, participants will have their breath tested (eCO) to assess compliance and physiologic data collection will begin. We will check blood pressure once at the beginning of the session and again at the end. Heart rate will be measured continuously throughout the session.

Approximately five minutes after session onset, participants will sample the session-specific product (4 puffs) followed by a 60-minute rest period. During this time participants will not be allowed to eat or drink outside beverages but we will provide water to drink and they are invited to use their phone, read books/magazines, or watch movies that we provide to them.

After the rest period, participants will complete baseline subjective measures 1 to assess tobacco abstinence symptoms. Immediately after subjective measures 1, two DPTs (session specific DPT, CP-DPT) will be completed. The DPTs take approximately 10 minutes to complete. Then the PRT will begin, which lasts for 30 minutes. Subjective measures 2 begins at 30 minutes post-PRT start. This should take approximately 5 minutes. After this participants will start the 2nd 60-minute rest period.

After the rest period, participants will complete subjective measures 3. This should take about 5 minutes. Then participants will start the CP-PRT, which lasts for 30 minutes. Subjective measures 4 begins at 30 minutes post-CP-PRT start.

When the CP-PRT and Subjectives measures 4 are completed, physio data collection will end and participants will be paid for their time. The study procedures for sessions 1 – 4 should take no more than 220 minutes or 3 hours and 40 minutes.

For the 5th session, participants will experience the same procedures except they will not complete the CP-DPT or CP-PRT. Thus study procedures for the 5th session should take no more than 185 minutes or 3 hours 5 minutes.

Please note there can be some variability in the session times due to participant behavior (i.e., taking shorter/longer than expected to complete measures/tasks).

Session Timeline:

0m – eCO Check; Physiologic data collection begins, additional questions asked.

5m – 4 sample puffs

10m – Begin 60m rest period

70m – Subjectives measure 1

75m – DPTs – 2: session specific DPT, CP-DPT with their own brand cigs

85m – PRT – 30 min

115m – PRT completed; Subjectives measure 2

120m – Begin 60m rest period

180m – Subjectives measure 3

185m – own brand session STOP

OR

185m – CP-PRT – 30 min

215m – CP-PRT completed; Subjectives measure 4

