220m – End session

Product administration will consist of 4 sample puffs at the beginning of each session. Four behavioral tasks will be performed (DPTs, CP-DPT, PRT, and CP-PRT) for sessions 1 – 4. The PRT and CP-PRT behavioral tasks may yield additional puffs from a session specific ECIG or their own brand cigarette. The CP-PRT and CP-DPT will not be performed in the own-brand session (session 5) but participants will be asked to complete the remaining two behavioral choice tasks (DPT and PRT). See the Behavioral Measures section below for more details.

Three months following the final in-person session, participants will be administered one follow- up survey via phone (verbally administered) or email (participant completes survey online) regarding their cigarette and e-cigarette use behaviors ('Follow-Up Survey').

Measures.

Baseline measures. During the in-person eligibility screening, we will assess sociodemographic information, risk taking,

discounting, health and psychiatric conditions, drug and alcohol use, history and patterns of tobacco use, nicotine dependence/craving, and perceived harm and risk of tobacco products using standardized items from national surveys (e.g., Behavioral Risk Factor Surveillance Survey; Tobacco Use Supplement to the Current Population Survey). We will also take pictures of participant's own brand cigarettes. Urine samples will be tested immediately for cotinine (a major nicotine metabolite) using the NicAlert semi-quantitative test (Jant Pharmaceutical Corporation, Encino, CA), and among women for pregnancy. We will also be obtaining baseline physiological measures including: eCO and HR/BP. eCO will be assessed via a BreathCO monitor (Vitalograph, Lenexa, KS). HR/BP will be measured and saved electronically using software and equipment that sounds an alarm if safety parameters are exceeded (Model 506, Criticare Systems).

Risk tasking and discounting tasks will only be administered to participants at baseline who appear eligible based on all the criteria assessed during the in-person screening. These two tasks will be the final assessments for participants who appear to be eligible at the in-person screening.

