3. On very rare occasions, you may experience small droplets of liquid during inhalation of the e-cigarette we provide. You may find these droplets to be unexpected and/or unpleasant. This experience has been reported by e-cigarette users, and they report that it is an annoyance that does not appear to present any known medical danger. If this occurs, we will immediately replace the e-cigarette device you are using.
4. The e-cigarette liquid that we give you may contain more nicotine than you are used to, although some e-cigarette users report using these liquids. Inform the study staff immediately if you experience any discomfort
5. You may also experience side effects from products that contain nicotine such as acute increases in heart rate and blood pressure, sweating, lightheadedness, dizziness, nausea, and nervousness. These side effects are unlikely in individuals who use cigarettes regularly.
6. The Centers for Disease Control and Prevention advises that e-cigarette, or vaping products are unsafe for youths, young adults, or women who are pregnant. Adults who do not currently use tobacco products should not start using e-cigarette, or vaping, products. If you use e-cigarette products, monitor yourself for the below symptoms and promptly seek medical attention if you have concerns about your health.
 - a. Some people who use e-cigarettes have reported experiencing seizures. Some of these individuals reported a prior history of seizures or using other substances at the same time as their e-cigarette.
 - b. In some cases, e-cigarette use has led to respiratory illnesses such as difficulties breathing, shortness of breath, cough, and/or chest pain before hospitalization. In some cases, e-cigarette use has led to death, although most of these cases have been related to vaping THC.
 - c. In some cases, e-cigarette use has been associated with symptoms of mild to moderate gastrointestinal illness such as nausea, abdominal pain, vomiting, diarrhea, fevers or fatigue.
7. The use of e-cigarettes may include other side effects/risks such as a sore or scratchy throat and headache.
8. E-cigarette devices will be reused for participants. New disposable mouthpieces will be provided to each participant. There is some risk of contamination or illness, which is minimized by sanitizing the e-cigarette devices in addition to the use of these mouthpieces.

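### Pregnancy is checked, as described, only at screening, with no described check before product is given at the five later sessions

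*Combined protocol and SAP*

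**What the plan says.** The eligibility rule in Study Population, item 5, is: "Women will be excluded if they are breast-feeding or test positive for pregnancy (by urinalysis) at the screening". Item 7 of the same section gives the reason: "We also exclude pregnant/breastfeeding women as tobacco/nicotine use is dangerous to a fetus/child". The other places that mention the test agree on its timing. Study Procedures, item 6, puts the urine sample in the in-person screening visit. Sample Collection Details, item 4, has urine collected at baseline screening and describes no later collection. Pertinent Results and Incidental Findings, items 2 and 5, has pregnancy assessed and its result communicated at screening.

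Study Procedures, item 6, describes the start of each of the five sessions. It says that "participants will be asked about symptoms experienced since last visit and their use of other substances in their ECIG". The timeline entry for minute 0 adds, without listing them, "Physiologic data collection begins, additional questions asked". At minute 5 comes product: "Product administration will consist of 4 sample puffs at the beginning of each session".

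Two other provisions bear on the point. The risk text in Behavioral Intervention/Task Details, item 2, tells participants that "e-cigarette, or vaping products are unsafe for youths, young adults, or women who are pregnant". The withdrawal criteria (Risks, Discomforts, Potential Harms and Monitoring, item 5) let the investigator or study nurse withdraw a participant over any safety concern, with blood pressure and heart rate as examples.

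**The concern.** The plan excludes pregnant women to keep tobacco and nicotine given by the study away from a fetus. All of that exposure happens after screening, at sessions 1 to 5. A negative urine test at screening says nothing about a pregnancy that begins or is recognised later. Participants are aged 18 to 55 and the plan says that "We will attempt to recruit an equal number of men and women of diverse racial/ethnic backgrounds", so women of childbearing age are expected.

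What is at stake is participant safety and consistency with the plan's own reason for exclusion. Power, estimation and the analysis are not affected.

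**Working it through.** No formula in the plan is in dispute. The check is a count of visits and a comparison of what each visit is described as containing.

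**Visits.** One in-person screening plus five product sessions: 1 + 5 = 6. The three-month follow-up is by phone or email, so it does not count.

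| Described check | Screening | Sessions 1–5 | Total |
|---|---|---|---|
| Pregnancy test or question | 1 of 1 | 0 of 5 | 1 of 6 |
| Respiratory and gastrointestinal symptom questions | 1 of 1 | 5 of 5 | 6 of 6 |
| Blood pressure | 1 of 1 | 5 of 5 (start and end) | 6 of 6 |

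The second row comes from Risks, item 2, and Study Procedures, item 6. The third comes from Study Procedures, item 6.

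**Age of the screening result.** The plan sets no maximum interval from screening to session 5. Under the withdrawal criteria, a session missed through failed abstinence can be rescheduled repeatedly with no fixed number of attempts. How old the negative test may be at the last session is therefore not bounded.

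**Required exposure.** Four sample puffs at each of five sessions gives 4 × 5 = 20. One session uses 0 mg/ml liquid, so 4 × 4 = 16 of these are puffs of a nicotine-containing product. Further puffs in the progressive ratio tasks are the participant's choice.

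**Where a question would fit.** Active Internet Data Collection, item 6, makes answers to the pre-session symptom questions mandatory. Those questions come at the start of the session, and the sample puffs about five minutes after it begins. A mandatory slot before first product use already exists.

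**Cost in answers.** The plan does not fix the number of women. Assuming 15, 20 or 25 women among the 40 completers, at five sessions each:

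- 15 × 5 = 75
- 20 × 5 = 100
- 25 × 5 = 125

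The true total would be slightly higher, because participants who begin sessions and are later replaced would also answer. The plan gives no figure for their sessions.

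**What cannot be derived.** The documents give no basis for the expected number of pregnancies, the usual interval from screening to session 5, or exposure net of the participant's own smoking.

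**The case against.** The strongest objection is that this is a claim of absence and the relevant files cannot be seen. The pre-session checklist is an approved study document that is not reproduced, the extra questions at minute 0 are not listed, and the consent pages were removed. Any of them might ask about pregnancy or tell participants to report it. This stands as a condition on the whole point. A reader might infer that the trial never asks again; the documents show only that no described step does. What is visible, a checklist titled for symptoms and described as respiratory and gastrointestinal, gives no sign of such a question.

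A reader might also infer that staff could not withdraw a participant who became pregnant. That is not supported. The safety provision is open-ended, its examples are only examples, and a known pregnancy falls within it.

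Nor does the point extend to breast-feeding. A woman who tests negative for pregnancy and is not breast-feeding at screening would ordinarily have to conceive and deliver before she could begin, which is nearly impossible during a five-session study. Repeating that question is not worthwhile.

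The comparison with symptoms and blood pressure is imperfect. Those are repeated because they may change acutely with product use, and no repeat is described for other entry exclusions such as psychiatric treatment or intention to quit. That is fair. The case for re-asking about pregnancy rests on the stated reason for exclusion, not on the 6-of-6 comparison.

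Finally, participants already smoke, sessions follow at least 12 hours of abstinence, and Risks, item 2, puts study exposure at or below ordinary use. This limits the expected harm. It does not remove the inconsistency, because the plan excludes pregnant smokers at entry despite the same argument.

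**Conclusion.** The point holds as a low-severity, inexpensive safety improvement. As described, pregnancy is checked at 1 of 6 in-person visits and at 0 of the 5 where product is given, with no limit on the time since screening. Followed as written, the plan would give product to a participant who knows that she is pregnant and does not say so.

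This rests on two conditions: that the unseen checklist does not already ask, and that the removed consent text does not already require participants to report a pregnancy. Confidence is medium for that reason.

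The benefit is confined to women who know that they are pregnant and would answer a direct question, but would not raise it themselves despite the warning in the risk text. A reader might infer appreciable added fetal exposure. The documents do not support that, since they allow neither net exposure nor the number of pregnancies to be estimated, and the participants are current smokers.

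**What to change.** First, check the pre-session checklist. If it already asks about pregnancy at every session, no new question is needed. If it does not:

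1. Add one pregnancy question for women to the mandatory pre-session questions, answered before the 4 sample puffs.
2. Send a positive or uncertain answer to the person who already reviews worsening symptoms, before any product is given. Treat a declined answer as uncertain.
3. Give no further product sessions to a participant who is pregnant, under the existing safety-withdrawal provision.

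The cost is about five short answers per woman attending all sessions, or slightly more than 75 to 125 in total under the assumption above. An occasional withdrawn participant would be replaced under the existing rule, which recruits until there are 40 completers. Self-report will miss a pregnancy that the participant does not yet know about.
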